***MANAGEMENT OF CARDIOVASCULAR irAES IN PATIENTS TREATED WITH ICPis***

10.0 Cardiovascular Toxicities	
10.1 Myocarditis, pericarditis, arrhythmias, impaired ventricular function with heart failure and vasculitis	
Definition: Signs and symptoms may include chest pain, arrhythmia, palpitations, peripheral edema, progressive or acute dyspnea, pleural effusion, fatigue	
Diagnostic work-up	
At baseline	
ECG	
Consider troponin, especially in patient treated with combination immune therapies Upon signs/symptoms (consider cardiology consult)	
ECG	
Troponin	
BNP Echocardiogram CXR	
Additional testing to be guided by cardiology and may include Stress test	
Cardiac catheterization Cardiac MRI	
Grading	Management
G1: Abnormal cardiac biomarker testing, including abnormal ECG	All grades warrant work-up and intervention given potential for cardiac compromise
G2: Abnormal screening tests with mild symptoms	Consider the following: For G1: Hold ICPi
G3: Moderately abnormal testing or symptoms with mild activity	For G2, G3, and G4: Permanently discontinue ICPi For G1-G4: High-dose corticosteroids (1-2 mg/kg of prednisone) initiated rapidly (oral or IV depending on symptoms)
G4: Moderate to severe decompensation, IV medication or intervention required, life-threatening conditions	Admit patient, cardiology consultation Immediate transfer to a coronary care unit for patients with elevated troponin or conduction abnormalities In patients without an immediate response to high-dose corticosteroids, consider early institution of cardiac transplant rejection doses of corticosteroids (methylprednisolone 1 g every day) and the addition of either mycophenolate, infliximab, or antithymocyte globulin
Qualifying statement: Treatment recommendations are based on anecdotal evidence and the life-threatening nature of cardiovascular complications. The appropriateness of rechallenging remains unknown. Note that infliximab has been associated with heart failure and is contraindicated at high doses in patients with moderate- severe heart failure.	
10.2 Venous thromboembolism	

M7824 Clinical Protocol v2.0 dated 01-Dec-2021

Definition: A disorder characterized by occlusion of a vessel by a thrombus that has migrated from a distal site via the blood stream. Clinical signs and symptoms are variable and may include pain, swelling, increased skin vein visibility, erythema, and cyanosis accompanied by unexplained fever for DVT and dyspnea, pleuritic pain, cough, wheezing, or hemoptysis for PE

Diagnostic work-up

Evaluation of signs and symptoms of PE or DVT may include Clinical prediction rule to stratify patients with suspected venous thromboembolism Venous ultrasound for suspected DVT

CTPA for suspected PE

Can also consider D-dimer for low-risk patients based on risk stratification by clinical prediction rule for DVT/PE when CT or Doppler are not available or appropriate Ventilation/perfusion scan is also an option when CTPA is not appropriate

Consider other testing, including ECG, CXR, BNP and troponin levels, and arterial blood gas

10.0 Cardiovascular Toxicities	
Grading	Management
G1: Venous thrombosis (eg, superficial thrombosis)	Continue ICPi Warm compress Clinical surveillance
G2: Venous thrombosis (eg, uncomplicated DVT), medical intervention indicated G3: Thrombosis (eg, uncomplicated PE [venous], nonembolic cardiac mural [arterial] thrombus), medical intervention indicated	Hold ICPi until AE reverts back to G1 or less. If reverts to G2, use benefit-risk assessment for ICPi continuation Consider consult from cardiology or other relevant specialties LMWH is suggested over VKA, dabigatran, rivaroxaban, apixaban, or edoxaban for initial and long-term treatment IV heparin is an acceptable alternative for initial use, and oral anticoagulants are acceptable for the long term
G4: Life-threatening (eg, PE, cerebrovascular event, arterial insufficiency), hemodynamic or neurologic instability, urgent intervention indicated	Permanently discontinue ICPi Admit patient and management according to CHEST, ACC, and/or AHA guidelines and with guidance from cardiology Respiratory and hemodynamic support LMWH is suggested over VKA, dabigatran, rivaroxaban, apixaban, or edoxaban for initial and long-term treatment IV heparin is an acceptable alternative for initial use, and oral anticoagulants are acceptable for the long term Further clinical management as indicated based on symptoms
Additional considerations  While it may be impossible to determine the etiology of thromboembolic disease in patients with advanced cancer and the role, if any, that ICPi treatment plays, it is reasonable to remove the potential inciting agents given the severity and life-threatening potential of G4 complications. Clinicians are to use clinical judgment and take into account the risks and benefits when deciding whether to discontinue ICPi treatment.  Anticoagulant therapy duration should continue for a minimum of 9-12 months to indefinitely in the setting of active cancer unless patient is asymptomatic, doing well, or in remission.  All recommendations are expert consensus based, with benefits outweighing harms, and strength of recommendations are moderate.	

Abbreviations: BNP, brain natriuretic peptide; CT, computed tomography; CTPA, computed tomography pulmonary angiography; CXR, chest x-ray; DVT, deep vein thrombosis; ECG, electrocardiogram; G, Grade; ICPi, immune checkpoint inhibitor; irAE, immune-related adverse event; IV, intravenous; LMWH, low-molecular-weight heparin; MRI, magnetic resonance imaging; PE, pulmonary embolism; VKA, vitamin K agonist.

***MANAGEMENT OF OCULAR irAES IN PATIENTS TREATED WITH ICPis***

11.0 Ocular Toxicities	

Counsel all patients to inform their health care provider immediately if they experience any of the following ocular symptoms
 
Blurred vision Change in color vision Photophobia Distortion Scotomas Visual field changes Double vision Tenderness Pain with eye movement Eyelid swelling Proptosis
	

Evaluation, under the guidance of ophthalmology Check vision in each eye separately Color vision Red reflex Pupil size, shape, and reactivity Fundoscopic examination Inspection of anterior part of eye with penlight
	

Prior conditions Exclude patients with history of active uveitis History of recurrent uveitis requiring systemic immunosuppression or continuous local therapy Additional considerations Ocular irAEs are many times seen in the context of other organ irAEs High level of clinical suspicion as symptoms may not always be associated with severity Best to treat after ophthalmologist eye examination
	
11.1 Uveitis/iritis	

Definition: Inflammation of the middle layer of the eye Diagnostic work-up: as per above
	
Grading	Management
G1: Asymptomatic	
Continue ICPi Refer to ophthalmology within 1 week Artificial tears

G2: Medical intervention required, anterior uveitis	
Hold ICPi temporarily until after ophthalmology consult Urgent ophthalmology referral Topical corticosteroids, cycloplegic agents, systemic corticosteroids May resume ICPi treatment once off systemic corticosteroids, which are purely indicated for ocular adverse effects or once corticosteroids for other concurrent systemic irAEs are

	reduced to $\leq$ 10 mg; continued topical/ocular corticosteroids are permitted when resuming therapy to manage and minimize local toxicity Re-treat after return to G1 or less
G3: Posterior or panuveitis	Permanently discontinue ICPi                   Urgent ophthalmology referral. Systemic           corticosteroids           and intravitreal/periocular/topical corticosteroids
G4: 20/200 or worse	Permanently discontinue ICPi                   Emergent ophthalmology referral

Abbreviations: ICPi, immune checkpoint inhibitor; G, Grade; irAE, immune-related adverse event; IV, intravenous, TNF, tumor necrosis factor.

### 5.6.6 Management of Adverse Skin Reaction

TGF- $\beta$  inhibition mediated skin reactions are considered important identified risk for bintrafusp alfa. Skin assessment must be performed at baseline and at least every 6 weeks during treatment and at the end of treatment or 28 ( $\pm 5$  days) days post-treatment safety follow-up (if not performed in the previous 6 weeks).

- Hyperkeratosis
- Keratoacanthoma
- Cutaneous squamous cell carcinoma (cSCC)
- Basal cell carcinoma
- Actinic keratosis

#### Management

- Baseline skin assessment with detailed medical history
- Discontinuation or termination not required in most cases. Continuation of treatment should be evaluated by the Investigator.
- Emollients may be used
- Develop diagnostic and treatment plan in collaboration with Investigator and dermatologist
- Treatment follow-up will depend on number and localization of lesions.
  - Single lesion: full excision may be recommended
  - Multiple lesion or location not suitable for full excision: Mohrs surgery, cryotherapy or other standard treatment options depending on pathology. Retinoids may be used after discussion with Investigator.
- Close clinical follow-up for re-evaluation, resolution and potential recurrence should be implemented
- In general, treatment of TGF- $\beta$  mediated skin lesions should be based on local guidelines/standard of care.

Additional consideration: Keratoacanthoma lesions may resolve spontaneously without surgical intervention within weeks after discontinuing bintrafusp alfa.

Consult with Medical Monitor as needed for management of TGF- $\beta$  mediated skin lesions.

### 5.6.7 Management of Treatment-Related Anemia

- Anemia is considered an important identified risk for bintrafusp alfa.
- Hematology assessment must be performed at baseline, prior to each bintrafusp alfa dose, at the end of treatment visit and at 28 ( $\pm 5$  days) days post-treatment safety follow-up.
- Participants must enter the study with Hgb values at least 9g/dl
- All relevant hematological testing for treatment-related anemias should be done prior to a blood transfusion, if clinically feasible

#### Basic Anemia Evaluation

- CBC with emphasis on red cell indices
- If indicated and at clinical discretion, the following should be considered:
  - Iron studies
  - Serum Folate and Vit B12 values
  - Coagulation factors
  - Fecal occult blood
  - Urinalysis
  - Hormone panel: TSH, Erythropoietin

 
○ Peripheral blood smear
 

Further Recommendation Based on Suspected Etiology (in Addition to Basic Anemia Testing)

 
● Suspected Hemolysis 
 
○ bilirubin, LDH, Coombs test, haptoglobin
 
 
 
● Suspected bleeding: 
 
○ Consider imaging/interventional radiology consultation as indicated
 
○ Consider imaging and/or endoscopy as clinically indicated
 
 
 
● Suspected aplastic anemia: 
 
○ Hematology consultation
 
○ Consider bone marrow aspiration/morphologic evaluation
 
 
 

Additional consideration:
 
In general, blood transfusions and erythroid growth factors are permitted as clinically indicated.

Abbreviation: CBC: complete blood count, TSH: thyroid stimulating hormone, LDH: lactate dehydrogenase

### 5.6.8 Management of Bleeding Adverse Events

Bleeding Adverse Events	

 
● Bleeding adverse events are considered important identified risk for bintrafusp alfa.
 
● In general, mild and moderate mucosal bleedings resolve without discontinuation of treatment.
 
● These events may include, but are not limited to the following: 
 
○ Epistaxis
 
○ Hemoptysis
 
○ Gingival bleeding
 
○ Hematuria
 
 
 
	
Mucosal/Non-tumor Bleeding	
Grading	Management
Grade 2	
 
● If resolves to Grade <math>\leq 1</math> by the day before the next infusion, study intervention may be continued
 
● If not resolved to Grade <math>\leq 1</math> by the day before the next infusion, but is manageable and /or not clinically relevant, consult Medical Monitor to assess if clinically reasonable to administer the following infusion.
 

Grade $\geq 3$	
 
● Permanently discontinue treatment unless an alternative explanation can be identified (such as concomitant use of antithrombotic agents, traumatic events, etc.)
 
● In case of alternative explanations, hold study treatment until the event recovers to Grade <math>\leq 1</math>
 

	
 
• If Grade <math>\geq 3</math> bleeding event is observed, regardless of causality with the study intervention, upon resumption of study intervention bintrafusp alfa dose should be reduced by 50% (600 mg Q2W for participants dosed with 1200 mg, 1200 mg for participants dosed with 2400 mg). Once there is stable resolution and no recurrence of bleeding on reduced dose, Investigator is encouraged to communicate with Medical Monitor on potential dose re-escalation after careful benefit-risk assessment.
 

Grade 4	
 
• Treatment must be permanently discontinued if no alternative explanation is identified.
 


In case of rapid decrease of hemoglobin (Hgb), such as a decrease greater than 2.0 g/dL across a 2 weeks period, withhold the subsequent cycles of study intervention until Hgb is stabilized and do a thorough assessment of bleeding (for example, upper and lower GI endoscopy, enhancement CT etc.); if Grade 1 or greater bleeding is observed or suspected, withhold the bintrafusp alfa until the bleeding is resolved/controlled and resume the dose of bintrafusp alfa reduced by 50%. Once Hgb decrease is recovered to <math>\leq</math> Grade 1 or baseline and stably controlled, the Investigator is encouraged to communicate with Medical Monitor to re-escalate the dose. The dose of bintrafusp alfa may be re-escalated to full dose once Hgb is stabilized without further need for blood transfusion in the subsequent cycles. The timing of re escalation may need a case-by-case decision. See Section Table 5 regarding stabilization of anemia.
	
Tumor Bleeding	
Grade $\geq 2$	
 
• Study treatment must be held till the event recovers to Grade <math>\leq 1</math>
 
• Permanently discontinue treatment if the Investigator considers the participant to be at risk for additional severe bleeding.
 

Grade $\geq 3$	
 
• If Grade <math>\geq 3</math> bleeding event had been observed, regardless of causality with the study intervention, upon resumption of the study intervention bintrafusp alfa dose should be reduced by 50%. Once there is stable resolution and no recurrence of bleeding on reduced dose, Investigator is encouraged to communicate with Medical Monitor potential dose re-escalation after careful benefit-risk assessment. Treatment should be permanently discontinued if the Investigator considers the participant to be at risk for additional severe bleeding.
 
• In case of rapid decrease of hemoglobin (Hgb), see Section Mucosal/Non-Tumor bleeding.
 

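### Section 5.6.8 gives two incompatible instructions, permanent stop and resume at half dose, for an unexplained Grade ≥3 mucosal bleed with a rapid haemoglobin fall

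*Protocol*

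**What the plan says.** Section 5.6.8, mucosal/non-tumor part, Grade ≥3: "Permanently discontinue treatment unless an alternative explanation can be identified", with antithrombotic drugs and trauma as examples of such an explanation. Where there is one, "In case of alternative explanations, hold study treatment until the event recovers to Grade" 1 or lower; the same row adds that "upon resumption of study intervention bintrafusp alfa dose should be reduced by 50" percent. The Grade 4 row says: "Treatment must be permanently discontinued if no alternative explanation is identified".

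A paragraph in the same table then sets a different trigger: "In case of rapid decrease of hemoglobin (Hgb), such as a decrease greater than 2.0 g/dL across a 2 weeks period". Cycles are withheld until haemoglobin stabilises and a search for bleeding is made. Then, "if Grade 1 or greater bleeding is observed or suspected, withhold the bintrafusp alfa until the bleeding is resolved/controlled and resume the dose", at a 50% reduction. Two sentences on returning to full dose follow, and then a pointer: "See Section Table 5 regarding stabilization of anemia".

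The Grade ≥3 row for tumor bleeding refers the reader to the mucosal/non-tumor part when haemoglobin falls rapidly. The whole table is repeated in section 5.6.5 under bleeding irAEs. Section 5.6.3 separately requires permanent discontinuation for Grade 3 and Grade 4 adverse drug reactions, with listed exceptions that do not include bleeding.

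**The concern.** The grade rows and the haemoglobin paragraph use different triggers, and a patient can meet both. For a severe mucosal bleed with no alternative explanation, the rows end treatment. The paragraph starts at Grade 1 with no ceiling and leads to re-treatment at half dose.

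Two investigators could each follow the table faithfully, one stopping the drug for good and the other giving it again after a severe bleed. Bleeding is described in 5.6.8 as an important identified risk and is an adverse event of special interest in 6.6.3, so this is a patient-safety matter. It also means that discontinuation for toxicity and exposure after a bleed would depend partly on which sentence the investigator followed. The table asks for a Medical Monitor consultation on unresolved Grade 2 mucosal bleeding and on re-escalation, but not on the half-dose resumption itself, so that step would not necessarily expose the conflict.

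**Working it through.** No sample-size, power or error-rate figure is involved, so the check is a reading of the two rules side by side.

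**Inputs (section 5.6.8, mucosal/non-tumor part)**

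- Rule A, Grade ≥3 and Grade 4 rows: permanent stop without an alternative explanation. With one, hold until Grade ≤1, then half dose on resumption.
- Rule B, rapid-haemoglobin paragraph: triggered by a rapid fall, with more than 2.0 g/dL in 2 weeks given as an example. If bleeding of Grade 1 or higher is seen or suspected, withhold, then resume at half dose.

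**Cases for a Grade ≥3 mucosal/non-tumor bleed**

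| Alternative explanation | Rapid fall | Rule A | Rule B | Result |
|---|---|---|---|---|
| No | No | Permanent stop | Not triggered | No conflict |
| No | Yes | Permanent stop | Withhold, resume at 50% | **Conflict** |
| Yes | No | Hold to Grade ≤1, 50% on resumption | Not triggered | No conflict |
| Yes | Yes | Hold to Grade ≤1, 50% on resumption | Withhold, resume at 50% | No stop-versus-resume conflict |

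The conflict arises in 1 of the 4 cases, and in 1 of the 2 with a rapid fall. These count types of case, not patients.

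**Is precedence stated anywhere?** Not in 5.6.8 or in its copy in 5.6.5. Section 5.6.3 points towards stopping if the bleed is judged an adverse drug reaction, but it does not say that it overrides the bleeding table.

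**Is the paragraph confined to lower grades?** No such limit is written, and the tumor-bleeding Grade ≥3 row sends readers to it.

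**Related wording in the same paragraph.** One re-escalation sentence depends on haemoglobin recovering to Grade ≤1 or baseline under stable control. The next depends on stability without further transfusion. How they relate is not stated. The pointer to Table 5 has no target: the only numbered table caption in the document is Table 1, and section 5.6.7 on anemia contains no stabilization criterion.

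**The case against.** The best defence is that the haemoglobin paragraph only adds a restriction. It opens by withholding later cycles, which presupposes that the patient still has cycles to receive; a permanently discontinued patient has none. It calls for a search for bleeding and covers suspected bleeding. Its practical effect would then fall on Grade 1 or suspected bleeding, which has no row of its own, and on Grade 2, where the table may allow treatment to go on. Section 5.6.3 agrees with the grade rows for Grade 3 and 4 drug reactions. This is a reasonable account of what the authors may have meant. But the text sets no upper grade, and the tumor-bleeding cross-reference brings Grade ≥3 events into the paragraph. That reference comes from a part of the table with no automatic stop, so it does not show that the paragraph overrides the mucosal rows. It does show that the paragraph is not reserved for mild bleeding.

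Some stronger readings are not supported:

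- A reader might infer that the more serious presentation gets the more lenient rule. That follows only if the paragraph overrides the grade rows, which the protocol does not say.
- A reader might take the two re-escalation sentences as rival triggers. They can also be read as consecutive steps: first a discussion with the Medical Monitor, then the return to full dose, with timing decided case by case.
- A reader might conclude that the safety data could not be interpreted. Section 6.6.6 has severity, causality and action taken recorded for every event, and repeat events documented anew, so what was done will be known.

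The missing table reference taken alone is editorial; section 5.6.4 likewise cites a Table 6.

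**Conclusion.** Wrong as written: an internal contradiction in a stated treatment-stopping rule. It is confined to Grade ≥3 mucosal/non-tumor bleeds with no alternative explanation and a rapid haemoglobin fall, and it appears in both 5.6.8 and 5.6.5. The conclusion rests on the literal wording, in which Grade 1 upward includes Grades 3 and 4, and on the absence of any precedence statement.

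Its frequency among the planned 38 patients cannot be derived. Section 5.6.1 lists anemia and epistaxis among effects seen in at least 10% of 630 treated patients, but without a split by grade. It gives no rate of Grade ≥3 bleeding, no share without an alternative explanation and no share with a rapid fall. A reader might infer that the overlap is the usual course of a severe bleed; the protocol has no figure for that. The point warrants correction because it concerns stopping versus re-exposure after a severe bleed, not because many patients are expected to be affected. Which rule should stand is a clinical decision outside this review.

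**What to change.** Reconcile the grade rows and the rapid-haemoglobin paragraph in 5.6.8, make the identical change in 5.6.5, and align both with 5.6.3:

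1. State which bleeding grades the rapid-haemoglobin paragraph governs.
2. State which rule takes precedence when the Grade ≥3 or Grade 4 row also applies and no alternative explanation is found.
3. State whether the two re-escalation sentences are successive steps or alternatives.
4. Replace the reference to Table 5 with the stabilization criterion itself.

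The sponsor's clinicians decide the content of each rule. While the passages are open, the half-dose provisions should also be reconciled with section 5.6.2, which rules out dose reductions; that is a separate point.

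The cost is a wording amendment to one paragraph and its copy, with no added patients, visits or tests.

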### **5.6.9 Alterations in Wound Healing or Repair of Tissue Damages**

- Impaired wound healing is considered important potential risk for bintrafusp alfa
- Management should be discussed with Medical Monitor for participants requiring surgery on study.  
It is recommended to hold study intervention for approximately 4 weeks post major surgery for observation. Post-operative wound healing should be closely monitored

### **5.6.10 Embryo-Fetal Toxicities**

Embryofetal toxicities are known risk of the PD 1/PD L1 targeting class and are considered important potential risks for bintrafusp alfa. Animal models link the PD 1/PD L1 signaling pathway with maintenance of pregnancy through induction of maternal immune tolerance to fetal tissue. Embryofetal toxicity is an important potential risk of bintrafusp alfa. An appropriate contraception warning is provided as part of the inclusion criteria. Pregnant and breastfeeding women are not allowed in the bintrafusp alfa study, and adequate contraceptive measures are recommended during the study to minimize or eliminate the potential risk to the developing fetus

### **5.6.11 Mild to Moderate Bleeding of the Mucous Membranes (Mucosal Bleeding Events)**

Mucosal bleeding of mild to moderate severity has been observed in patients treated with bintrafusp alfa in ongoing studies and is a potential risk of bintrafusp alfa. This type of bleeding may include nosebleeds, cough with blood in the phlegm (sputum), bleeding of the gums (gingival bleeding), or blood in the urine, among others. In general, this bleeding resolves without stopping treatment.

